17.5	Notification and reporting of Serious Adverse Events.....	32
17.6	Urgent Safety Measures.....	32
17.7	Annual Safety Reporting	33
17.8	Overview of the Safety Reporting responsibilities.....	33
18.	Monitoring and auditing	33
19.	Trial committees	33

20.	Finance and funding	33
21.	Indemnity.....	33
22.	Dissemination of research findings	33
23.	References	34

2. Glossary

CGM – continuous glucose monitoring

CBG – capillary blood glucose

3. Signature page

Chief Investigator Agreement	

The study as detailed within this research protocol will be conducted in accordance with the principles of Good Clinical Practice, the UK Policy Framework for Health and Social Care Research, and the Declaration of Helsinki and any other applicable regulations. I agree to take responsibility for the statistical analysis and oversight of this study.
	
Chief Investigator Name:	[name]
Signature:	
Date:	17/6/19.

4. Summary and synopsis

Short title	CGM use in diagnosis of spontaneous hypoglycaemia
Methodology	Clinical trial studying a novel intervention in clinical practice
Research sites	St Bartholomew's hospital
Objectives / aims	
Objectives
 
 1) Use CGM (blinded to the patient and investigator) in advance of standard investigations (where possible) in order to record whether patient symptoms correlate with recorded hypoglycaemia. This may exclude hypoglycaemia as a cause of symptoms and allow the patient to avoid a prolonged inpatient investigation. 2) Use CGM technology (blinded to the patient and investigator) alongside standard investigations for patients with both reactive and spontaneous hypoglycaemia to see if there is additional value in using two methods in detecting hypoglycaemic episodes. 3) Use CGM (blinded to the patient and investigator) to record frequency of hypoglycaemia after medical treatment has been initiated in order to assess its effectiveness in detecting hypoglycaemic episodes of which the patient may not have been aware, potentially reducing the need for painful finger prick glucose testing. 4) Use CGM (unblinded) to titrate medication to abolish

	
hypoglycaemia in order to improve outpatient management and improve patient safety. The Dexcom system has an alarm to alert patients to hypoglycaemia which will be used in the unblinded phase.
 
Aims
 
There will be two main arms to the study;
 
 1) Investigation of patients suspected of having hypoglycaemia (spontaneous or reactive) alongside standard investigations 2) Management of patients with confirmed hypoglycaemia who are medically managed to see if continuous glucose monitoring can play a role in abolishing asymptomatic hypoglycaemia through optimisation of medicines.
Number of participants	30
Inclusion and exclusion criteria	
Inclusion Criteria
 
Able and willing to give informed consent. No vulnerable adults will be included.
 
Either conventional gender, or non-binary.
 
Age >18 years
 
Any ethnicity
 
Any socio economic group
 
Medical condition as detailed above – arm 1 under investigation for possible/probable hypoglycaemia
 
Arm 2 – on medical therapy for established hypoglycaemia
 
Exclusion criteria
 
Unwilling or unable to give consent
 
Unable to speak sufficient English to give consent and understand study requirements
 
Age<18 or >90 years
 
Lack of capacity to consent
 
Underlying hepatic condition
 
Current excessive alcohol consumption (men regularly consuming >50 units/week, women >35 units/week)
 
Diabetes Mellitus
 
Current use of Diabetic medication or insulin
 
Currently pregnant
 
Any patient on haemo or peritoneal dialysis

Statistical methodology and analysis (if applicable)	
Study duration	1 year

5. Introduction

Suspected reactive and spontaneous hypoglycaemia can be a challenging problem to investigate. Definitive diagnosis currently relies upon the patient experiencing symptoms, reporting them accurately and then a series of complex investigations.

Current standard of care tests

Current 'gold standard' testing when reactive hypoglycaemia is suspected is with an extended oral glucose tolerance test or mixed meal test. Where spontaneous hypoglycaemia is suspected and where facilities exist, the 'gold standard' test is an admission to Hospital for a 72 hour fast with twice daily laboratory measurements of plasma glucose, insulin and c-peptide. Finger prick glucose measurements are taken throughout the day to check for asymptomatic hypoglycaemia. Additional laboratory measurements are made if the patient becomes symptomatic. The prolonged fast is terminated when a diagnostic laboratory glucose measurement of $<2.2\text{mmol/L}$ is reached. Where a 72 hour fast is not possible, attempts are made to test insulin and glucose after three separate 15 hour fasts but this risks out of hospital hypoglycaemia and all its potential sequelae. These investigations attempt to mimic the situations which precipitate the hypoglycaemia but, in particular for reactive hypoglycaemia, often fail to do so.

Pathophysiology and significance of hypoglycaemia

Symptomatic reactive hypoglycaemia is recognized in some patients with insulin resistance before the development of type 2 diabetes and is increasingly recognized as a complication of significant weight loss following bariatric surgery. Spontaneous hypoglycaemia is most commonly caused by an insulinoma which is a very rare diagnosis outside the context of MEN1 (1-4/million patients). In patients with MEN1, insulinoma is the second most common functioning pancreatic islet cell tumour (10-30%) (1) and typically occurs before the age of 40. In MEN1, the management of an insulinoma is the most challenging as: 1) Hypoglycaemia may be under reported as long term exposure to hypoglycaemia can result in hypoglycaemic autonomic failure with blunting or loss of the body's sympathetic response (loss of hypoglycaemic awareness) and an inability to counter-regulate subsequent or more serious events (2), including the possibility of sudden death (probably through cardiac arrhythmia) (3-5). 2) The chances of successful surgical resection and cure are lower as almost all MEN1 patients have multiple pancreatic lesions, many of which are smaller than the resolution of current imaging modalities. It can be difficult or impossible to know which lesion is producing insulin and extensive surgery can lead to pancreatic insufficiency to a degree that leaves the patient with extremely difficult to manage diabetes. As such patients are therefore often given medical therapies; these however are difficult to monitor for effectiveness, especially if there is loss of hypoglycaemic awareness.

Current testing limitations

Finger-prick glucose testing is currently the only viable way of home testing. Asymptomatic nocturnal hypoglycaemia is of most concern as repeat episodes are likely to lead to cumulative long term consequences of cerebral hypoglycaemia. Finger prick testing is unpopular amongst patients – it is painful and requires disposal

of 'medical sharps'. It also only provides a 'snapshot' of the patient's glycaemic state and so will, by its very nature; only provide this 'snapshot' when the patient is awake and able to use it.

Continuous glucose monitoring

CGM technology has transformed the monitoring of patients with diabetes mellitus who are insulin treated, particularly those affected by asymptomatic hypoglycaemia. The Dexcom system, which we will use for this study has performed favourably against competitors in the hypoglycaemic ranges in a head to head comparison study (6) and in a study examining the accuracy of the G6 device specifically (7). When using concomitant gold standard YSI glucose measurements as reference, for blood glucoses of <54mg/dL (3mmol/L) the G6 device was within 30% of the reference value 93.5% of the time and within 20% 85% of the time. For blood glucoses 54-69mg/dL (3-3.9mmol/L) these figures were 94.4 and 97.7% respectively (7).. Each system is composed of an implantable sensor (which can easily be placed by the patient) with a small probe that sits just under the skin and a chip which sits outside, all held in place by a dressing. Dexcom devices have enabled the instantaneous measurement of a surrogate of the capillary blood glucose simply by waving a mobile device (a proprietary device, or more recently a mobile phone or tablet) over the sensor. In addition to providing a 'stat' CBG reading, these devices can give quarter-hourly CBG readings for the entire life time of a sensor, data which can be downloaded onto a mobile device for later analysis. The Dexcom G6 device also allows the real time CBG readings to be shared 'live' with up to five people, providing additional safety and reassurance. In the context of reactive and spontaneous hypoglycaemia titration of anti-hypoglycaemia medication could be made through virtual consultations during the monitoring period.

5.1 Background

See above

5.4 Rationale

Prompt diagnosis of hypoglycaemia is important as, untreated, it can lead to weight gain, symptomatic hypoglycaemia and increases the risk of sudden death through arrhythmia. At present, diagnosis of hypoglycaemia depends upon the reporting of symptoms and capture of hypoglycaemic range CBGs through finger prick glucose measurement. If the clinical suspicion of hypoglycaemia is strong enough, then patients will be admitted for a supervised 72 hour fast, where blood glucose is checked regularly through finger prick measurements and venous phlebotomy. Patients can lose hypoglycaemic awareness, however, and so symptoms are not always a reliable way to diagnose the problems. 72 hour fasts are labour intensive for the medical and nursing teams and may require the patient to take time off work or away from caring duties. A robustly tested CGM test may allow us to determine if blinded CGM testing can be used to obviate the need for inpatient testing. It may also provide useful diagnostic information by relating the proximity of hypoglycaemic episodes to food intake, adding to weight to diagnoses of reactive or spontaneous hypoglycaemia.

CGM has revolutionized the lives and medical management of type 1 Diabetes patients with hypoglycaemic unawareness and we hope that it can produce similarly excellent results in the field of reactive/spontaneous hypoglycaemia.

Once spontaneous hypoglycaemia has been diagnosed, treatment with medical therapy is often the first step. The goal is to try and make the patient hypoglycaemia free. This is tricky if the patient has no hypoglycaemia awareness, but can be overcome during the day with regular fingerprick glucose checks – though patients frequently complain that this is painful. At night, however, patients are asleep and

cannot check their blood glucose this way and so there is a paucity of data about their glycaemic state at night – the very time that they are fasting and hypoglycaemia is more probable. CGM can therefore tell us about their glycaemic status all day, without painful finger prick testing and also during the night whilst the patient is asleep. This information can then help doctors titrate their anti-hypoglycaemia medication with the aim of abolishing their hypoglycaemic episodes.

5.5 Risks / benefits

Risks/inconveniences

Patients will have a glucose monitoring probe inserted, this sits on the abdominal wall and protrudes just under the skin, sampling the glucose in the interstitial fluid. There is sometimes a very small amount of discomfort associated with this (84% of users state it is painless in company's literature) and sometimes a very small amount of inconvenience associated with wearing it if it catches on clothing - but it is very slim and rarely interferes with normal day-to-day activities.

CGM sensor/transmitter is fully waterproof and can be worn in showers/baths and also to the gym.

CGM system is safe to travel with. We will provide a letter explaining the system's components if study participants wish to fly in order to clear airport security.

Patient will wear a glucose monitoring sensor and data will wirelessly download to their mobile device or a proprietary glucose data receiver device. If the patient does not have a suitable mobile device then we will lend them a glucose data receiver.

CGM probe is inserted through the skin and so there is a theoretical risk of local infection if the skin is not cleaned prior to insertion as recommended.

There is a theoretical risk of the probe component breaking off under the skin.

Benefits

Discovery of hypoglycaemia earlier than would otherwise be the case.

Easier detection of asymptomatic hypoglycaemia in patients with known hypoglycaemia and therefore optimal titration of their medication.

Elimination of dangerous asymptomatic hypoglycaemia.

6. Study objectives

6.1 Primary objective

- 1) Use CGM (blinded to the patient and investigator) in advance of standard investigations (where possible) in order to record whether patient symptoms correlate with recorded hypoglycaemia. This may exclude hypoglycaemia as a cause of symptoms and allow the patient to avoid a prolonged inpatient investigation.
- 2) Use CGM technology (blinded to the patient and investigator) alongside standard investigations for patients with both reactive and spontaneous hypoglycaemia to evaluate the relative efficacy of the two methods in detecting hypoglycaemia episodes.
- 3) Use CGM (blinded to the patient and investigator) to record frequency of hypoglycaemia after medical treatment has been initiated in order to assess its

effectiveness in detecting hypoglycaemic episodes of which the patient may not have been aware, potentially reducing the need for painful fingerprick glucose testing.

4) Use CGM (unblinded) to titrate medication to abolish hypoglycaemia in order to improve outpatient management and improve patient safety. The Dexcom system has an alarm to alert patients to hypoglycaemia which will be used in the unblinded phase.

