6.3 Primary endpoint

Arm 1 -

Outpatient - CGM findings reflect patient's fingerprick glucose readings

- Episodes of true hypoglycaemia (as decided by finger prick glucose testing) are captured by the CGM device

- CGM detects hypoglycaemia whilst patient is asleep

Inpatient - 72 hour fast - CGM device calls hypoglycaemia when fingerprick/lab glucoses also do

Arm 2 -

Blinded phase - CGM findings reflect patient's fingerprick glucose readings - any episodes of true hypoglycaemia (as decided by fingerprick glucose testing) are captured by CGM device

unblinded phase - CGM recordings help with titration of anti hypoglycaemic medications and this reduces overall incidence of hypoglycaemic episodes or duration of time spent in hypoglycaemic range

For patients experiencing asymptomatic hypoglycaemic episodes, a reduction in asymptomatic hypoglycaemic episodes and regaining of hypoglycaemic symptoms.

For patients with symptomatic hypoglycaemia, a reduction in symptomatic episodes.

7. Study population

Clinicians in the endocrinology department at St Bartholomew's hospital will be notified of this study and encouraged to refer forward suitable patients from their clinics.

Arm 1

Patients referred to the endocrinology department at St Bartholomew's hospital for investigation of suspected hypoglycaemia by either GPs or other clinical teams in the same or external NHS trusts will be referred onwards to the study team by the doctor that sees them for their routine clinical care.

Arm 2

Patients known to the endocrinology department at St Bartholomew's hospital with hypoglycaemia that are medically managed or who are to start medical management will be referred to the study team by the doctor that sees them for their routine clinical care.

Some patients who are found to have hypoglycaemia through arm 1 of this study will be automatically offered the chance to partake in arm 2 if they are to have medical treatment.

No vulnerable groups will be included – all patient will be able to give valid consent on their own behalf
All patients will be able to understand sufficient English to give informed consent on their own behalf.

Inclusion Criteria

Able and willing to give informed consent. No vulnerable adults will be included.
Either conventional gender, or non-binary.
Age >18 years
Any ethnicity
Any socio economic group
Medical condition as detailed above – arm 1 under investigation for possible/probable hypoglycaemia

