12.2 Method of analysis

P<0.05 will be considered statistically significant

Arm 1

Positive and negative predictive value of CGM diagnosis of hypoglycaemia as an outpatient or an inpatient vs 72 hour fast (considered the 'gold standard')

Arm 2

In each patient, comparison of number of episodes of hypoglycaemia by finger prick glucose vs CGM vs symptoms during CGM blinded phase.

Severity of hypoglycaemia excursions

Amount of time spent in the hypoglycaemic range after medication titration – as measured by area under the curve on a time vs glucose graph generated by CGM machine. Comparisons of mean hypoglycaemic frequency and time within hypoglycaemic range within patients (blinded vs unblinded phase) using paired T test.

Change in hypoglycaemia questionnaire score before/after CGMs monitoring and medication titration

Regain of symptomatic hypoglycaemia in patients with asymptomatic hypoglycaemia, reduction of symptomatic hypoglycaemia in other patients.

13. Ethics

- Informed consent

Patients will be offered the chance to partake in the study should their treating consultant feel that they meet the inclusion criteria. Declining an invitation to take part in the study or leaving at any time means that the patient will default back to standard of care investigations. Their care will not be prejudiced or compromised in any way through either taking part or not taking part in the study.

- Recruitment

Only patients under investigation/treatment for hypoglycaemia at St Bartholomew's hospital will be considered for entry to the study. Patient being treated/investigated elsewhere who wish to be considered for the study would need to have their care transferred to St Bartholomew's by their GP/current endocrinologist.

- Inclusion / exclusion criteria

Inclusion/exclusion criteria is intended to screen out patients who have conditions that may affect their blood glucose (Diabetes Mellitus, underlying hepatic pathology) or in whom CGM is not recommended (pregnancy, critical illness) or in whom hypoglycaemia may be caused by extrinsic factors such as Diabetes medication.

- Study design

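### Primary objective 2 is put as two different questions, and the arm 1 inpatient endpoint and predictive values can show CGM agreeing with or losing to the standard work-up, but not beating it or adding to it

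*Protocol*

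**What the plan says.** Objective 2 concerns blinded CGM worn alongside standard investigations in patients with reactive or spontaneous hypoglycaemia. Section 6.1 ends it with the aim to "evaluate the relative efficacy of the two methods in detecting hypoglycaemia episodes". The synopsis (section 4) opens the objective in the same way but ends it "to see if there is additional value in using two methods in detecting hypoglycaemic episodes".

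The arm 1 endpoints in 6.3 are:
- inpatient: "CGM device calls hypoglycaemia when fingerprick/lab glucoses also do";
- outpatient: "Episodes of true hypoglycaemia (as decided by finger prick glucose testing) are captured by the CGM device", and separately "CGM detects hypoglycaemia whilst patient is asleep".

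The arm 1 analysis in 12.2 is "Positive and negative predictive value of CGM diagnosis of hypoglycaemia as an outpatient or an inpatient vs 72 hour fast (considered the 'gold standard").

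The introduction says that the standard investigations try to mimic the circumstances that bring on hypoglycaemia but "in particular for reactive hypoglycaemia, often fail to do so". It also names a different reference for reactive cases: "Current 'gold standard' testing when reactive hypoglycaemia is suspected is with an extended oral glucose tolerance test or mixed meal test".

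**The concern.** The two versions of objective 2 need different summaries. A test can detect fewer episodes than its comparator and still add value, because it finds different ones. It can also detect more and add little. A statistical analysis plan can specify how to answer a question, but it should not have to decide which question the protocol's primary objective asks.

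The inpatient endpoint and the arm 1 analysis fit neither version well, because both treat the standard investigation, one of the two methods compared, as the truth. Episodes that CGM finds and the standard work-up misses earn no credit in the endpoint and count against CGM in the positive predictive value. Section 5.4 gives asymptomatic and night-time lows as a main reason for using CGM, so the result could understate the benefit that the trial is meant to explore.

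The inpatient endpoint also joins finger prick and laboratory glucose with a slash. It does not say which governs when they disagree.

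**Working it through.** **Step 1: which cells the plan uses.** Cross-classify episodes (or patients; the argument is the same) as a = both methods positive, b = CGM only, c = standard only, d = neither.
- Inpatient endpoint (6.3): a/(a+c). Cell b does not enter.
- Positive predictive value (12.2): a/(a+b). Cell b enters only as false positives.
- Negative predictive value (12.2): d/(c+d). Cell b does not enter.
- Relative detection (6.1 wording) needs (a+b)/(a+c), with the b episodes verified.
- Added value (synopsis wording) needs verified b set against a+c.

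With the standard as truth, its own sensitivity is (a+c)/(a+c) = 1. The apparent CGM-to-standard ratio is a/(a+c), which cannot exceed 1. This ceiling needs no assumption about errors.

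**Step 2: how much this could hide.** The protocol gives no detection rates, so these are assumptions: the standard detects 70% of true episodes, CGM detects 85%, they do so independently, and neither gives false alarms.
- a = 0.70 × 0.85 = 0.595; b = 0.30 × 0.85 = 0.255; c = 0.70 × 0.15 = 0.105.
- True ratio: 0.85/0.70 = 1.21. Apparent ratio: 0.595/0.70 = 0.85.
- Apparent positive predictive value: 0.595/0.85 = 70%, although every CGM call is correct.
- Yield of either method: 0.595 + 0.255 + 0.105 = 95.5%, which the plan does not measure.

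With the standard at 50% to 90% and CGM at 70% to 95%, the true ratio runs from 0.70/0.90 = 0.78 to 0.95/0.50 = 1.90. The apparent ratio stays at 0.70 to 0.95, and the apparent positive predictive value runs from 50% to 90%.

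**Step 3: does an imperfect reference make CGM look worse?** Take finger prick as the only reference and assume that 20% of samples are truly low, with meter sensitivity 85% and specificity 95%, and CGM sensitivity 90% and specificity 95%.
- P(meter low) = 0.2 × 0.85 + 0.8 × 0.05 = 0.210.
- Independent errors: P(both low) = 0.2 × 0.85 × 0.90 + 0.8 × 0.05 × 0.05 = 0.155. Apparent CGM sensitivity = 0.155/0.210 = 74%, against a true 90%.
- Least possible overlap: (0.2 × 0.75)/0.210 = 71%, where 0.75 = 0.85 + 0.90 − 1.
- Greatest possible overlap: (0.2 × 0.85 + 0.8 × 0.05)/0.210 = 100%.

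With the same marginal accuracy, apparent sensitivity can fall anywhere from 71% to 100%. Both the direction and the size of the bias depend on how CGM and meter errors are correlated, and the protocol gives nothing on this.

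**Step 4: the reference for reactive patients.** Objective 2 covers reactive hypoglycaemia, but 12.2 uses the 72 hour fast for all of arm 1, and the introduction names another test for reactive cases. A reactive patient with real lows on CGM and a negative fast would be counted as a CGM false positive.

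**The case against.** The strongest case against has five parts.

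- **Comparing a new device with the accepted reference is conventional**, and 12.1 describes a 30-patient feasibility pilot. Agreement with the reference bears directly on a stated purpose, avoiding inpatient tests. This stands, and it limits how serious the point is.
- **The data are not lost.** Section 8 plans to match CGM with finger-prick and laboratory readings to check concordance, so discordant pairs can be tabulated, and an analysis plan not seen here may do so. This stands for the data. It does not settle which question objective 2 asks, or change the summaries fixed in 6.3 and 12.2.
- **Other parts touch on added value.** The sleep endpoint is not tied to finger prick, and arm 2 counts episodes by finger prick, CGM and symptoms side by side. Both are true, but the sleep endpoint is outpatient and names no comparator, and the arm 2 count serves objective 3.
- **The inpatient endpoint does not itself count CGM-only lows as errors.** Correct: it runs in one direction and ignores them. Only the positive predictive value penalises them.
- **Venous glucose is part of the standard investigations**, so it is not an independent referee between CGM and the whole work-up. Correct: it can referee only between CGM and finger prick. Most CGM-only lows will fall where no sample was taken.

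A reader might infer that neither version of objective 2 can be answered at all. The protocol does not support that, because arm 1 can show how often CGM agrees with or misses what the standard finds. A reader might also infer that the reported accuracy of CGM must be biased downwards. Step 3 of the working shows that this holds under independent errors but not in general.

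**Conclusion.** The point holds in a limited form. Objective 2 is worded as two different questions in current text. The inpatient endpoint and the predictive values against the fast can show agreement with the standard work-up or loss against it, but not superiority or incremental yield. That follows from the structure alone and rests on no numerical assumption.

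The sizes are illustrations. A true detection ratio of 1.21 appearing as 0.85 rests on assumed detection rates, independence and no false alarms. The 74% apparent sensitivity is one scenario, with independent errors and a meter-only reference, within a range of 71% to 100%.

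This should be put right because it concerns a primary objective and the remedy is cheap. It does not invalidate the pilot.

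**What to change.** 1. Use one wording of objective 2 in the synopsis and in 6.1. If both questions are wanted, state both in both places.
2. In 6.3 and 12.2, at times with a venous laboratory glucose, make the laboratory value the reference. Classify both CGM and finger prick against it. Report the sensitivity and specificity of each and the paired difference, using a method that allows for several samples per patient.
3. Report the full cross-classification of episodes: both methods, CGM only, standard method only.
4. List CGM-only lows without a simultaneous laboratory sample, such as nocturnal or asymptomatic ones, separately as unadjudicated rather than as false positives.

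The cost is wording in four places (synopsis, 6.1, 6.3 and 12.2). Section 8 already provides for venous glucose twice daily and at symptoms during admission, and for matching it with the other readings, so no extra samples are needed.

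There are two limits. Laboratory-referenced lows will be few and mostly at scheduled or symptomatic times, so the results will be descriptive. The laboratory-referenced comparison is also CGM against finger prick only; evidence of added value over the whole standard work-up will rest on the CGM-only listing.
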